Eligibility criteria. In addition to the eligibility criteria listed in Aim 1 – End-User Usability Testing, we will also include the following eligibility criteria: 1) understand the limitations of the OraQuick test and the mLab App (e.g., a confirmatory test is needed – see Protection of Human Subjects); 2) not having been tested for HIV in the past 6 months (e.g., therefore being somewhat outside of the current CDC testing recommendations for high-risk populations – see below). 3) not currently taking PrEP and 4) receive a non-reactive result on the rapid HIV test at the baseline visit

Alternatives and Potential Limitations. *We carefully considered the frequency of testing for our study participants and have agreed that participants should test at least every 3-6 months based on the following 2 considerations:* 1) Current CDC guidelines recommend annual testing and more frequent (every 3-6 months) for sexually active MSM at high-risk for HIV infection based on individual risk factors.^{129, 130} 2) Since all of our participants meet the criteria for use of PrEP¹⁰⁷ and based on our clinical experience for interpretation of these guidelines, we have specified that our study participants should test a minimum of every 3-6 months.^{27,28} As part of the intervention, participants in arm 1 will be reminded to use the OraQuick tests at 3 month, 6 month, 9 month, and 12 month time points through the mLab app.

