Study Enrollment. Study participants will come in to our study site in NYC or Chicago to provide informed consent, enroll, and complete a self-administered baseline survey on an iPad. Prior to enrollment into the RCT participants will be consented to screen and administered a rapid HIV test to determine eligibility. If a participant is found to be preliminary positive in the screening procedures they will be linked to care at NYP in New York or Lurie Children's Hospital in Chicago or a healthcare provider of their choice. If they are non-reactive they will be randomized and enrolled into the trial. The baseline survey will include questions on demographic characteristics; health literacy¹³¹; sexual risk behaviors including number of men (and women) they engaged in anal or oral sex with, condomless anal intercourse, as well as their HIV testing history and opinions regarding HIV testing. The baseline survey will also include questions on PEP/PrEP use and adherence, drug and alcohol use,¹³² and the HIV Risk Index.¹³³ After completing the baseline survey, study participants in all three study arms will receive condoms, an information sheet on HIV prevention, PrEP assessment, referral information for clinics that provide PrEP, and a card with the study team's contact information and the NYP/Columbia Comprehensive Care Clinic Phone/Text Number (NYC) and Northwestern/Lurie Children's Hospital (Chicago).

Randomization. After providing informed consent, youth will be randomized to study arms in a 2:2:1 ratio of : arm 1-mLab App (2), arm 2-Standard of Care HIV information arm (2), arm 3-HIV home tests (1). We will use

stratified randomization¹³⁴ to ensure equal representation between treatment groups at each study site (Chicago vs. NYC).¹³⁵ To reduce opportunities for selection bias, we will use a variable permuted randomization block design¹³⁶ where the block size itself is randomly selected (i.e., blocks of five to ten). The advantage of the permuted block design is that treatment assignment is pre-determined before the trial begins and then assignment remains static throughout the course of the trial.¹³⁷ Within each city stratum, a computer program will randomly assign each participant to the next treatment allocation from a random-permuted block randomized sequence. All **three arms** will receive standard-of-care HIV/STI testing-related risk reduction counseling, a box of condoms, PrEP assessment, and referral information for clinics that provide PrEP.

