Alternatives and Potential Limitations. Given that participants must be HIV negative to participate in the study, HIV testing will be included as the final screening component to verify study status prior to enrolling. This will help ensure that participants are not falsifying information on their screeners to enroll in the study. Importantly, participants are expected to continue normal healthcare activities during the course of the study and to be offered HIV testing referral information and on-site testing through existing service providers.

Arm 2- Standard of care HIV information control arm. Youth will receive standard-of-care HIV/STI testing-related risk reduction counseling, a box of condoms, PrEP assessment, and referral information for clinics that provide PrEP during your first visit. Youth randomized to arm 2, standard of care control, will be sent an email or text with links to mobile-optimized online prevention information, including PrEP and HIV testing information that is found on the CDC website.¹²⁷ They will also receive a study information card listing the Columbia University School of Nursing / Lurie Children's study teams' contact information. Once youth are randomized, they will be analyzed according to their original assignment (i.e., intent-to-treat).

Arm 3-HIV home testing arm. Youth randomized to arm 3 will be provided with the 2 OraQuick tests (including the package insert), and a box of condoms to take home at baseline. They will receive 2 more OraQuick tests at the 6 month visit. Participants may come in person to receive their tests or their tests may be mailed to them at their verified address if they are unable to complete an in-person 6 month visit. OraQuick tests will be sent via tracked shipping through USPS, FedEx, UPS. At their baseline appointment, youth will also be sent an email or text with links to mobile-optimized online prevention information, including PrEP and HIV testing information that is found on the CDC website. They will also receive a study information card listing the Columbia University School of Nursing / Lurie Children's study teams' contact information

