Reminder notifications. Participants in the intervention arm will be instructed to use the mLab App and the HIV self-test kit at 3 months, 6 months, 9 months, and 12 months after enrollment. Participants will receive a reminder push notification 2 weeks prior to their scheduled test date and 1 week after their scheduled test date.¹³⁸ In the mLab app, if a participant indicates they have received a preliminary positive HIV test using the home HIV test, participants will be directed to another screen on their smartphone directing them to call the study team or the warm line at the NYP or Lurie clinic (depending on geographic location) to receive follow-up confirmatory testing [and if needed, linkage to care]. Participants will be told that this result does not necessarily indicate that they are HIV positive (see false positive in Protection of Human Subjects), that further follow-up testing is needed, and they should contact the clinic or the study team within 24 hours. The mLab team will return the call within normal business hours. The number and nature of calls from participants to the study team (e.g., related to mLab App use, test interpretation, distress at reactive results) will all be recorded and will be reviewed yearly or at a date determined by the DSMB with our DSMB (see letters of support). We will track linkage to follow-up testing and care. Our DSMB will carefully monitor our study activities and data – see Data Safety and Monitoring Plan. **Sound Retention Efforts.** Participants will be asked after study screening what would be the best way for us to remind them of the appointment (voice phone, text, e-mail). Participant retention during the intervention will be enhanced in several ways. First, participants will be compensated for their time to complete the baseline assessment and completing the follow-up assessments. In addition, during the follow-up survey (6 months), participants will be asked to update their locator information. Using these extensive procedures promotes participant attendance at the follow-up visits, which has been shown to be successful in previous trials.^{139, 140} **We have 4 levels of outcomes:** primary, secondary, intermediate, and program evaluation. The survey items are included in the Qualtrics attachment. The primary outcome for Aim 2 / study trial (Uptake of rapid HIV

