self-testing) is the proportion of participants who self-report being tested for HIV in the past 6 months. The secondary goal is to collect and analyze data on the app's test interpretation performance. For the intervention arm (arm 1), we will also have data to confirm their self-report since we will have a photo image of their OraQuick test. We will assess and describe any bias in self-report of HIV testing in the intervention condition.

Follow-Up Surveys. All participants will receive a follow-up survey at 6 and 12 months after the baseline visit. The follow-up survey will be administered either in person on an iPad or, if they are unable to complete an in-person visit, remotely through a Qualtrics survey distributed via email. In total there will be three survey time points for all study participants (baseline, 6 and 12 months). Study participants will receive \$40 at baseline, \$55 at 6-month follow up, and \$75 at 12-month follow up for the time to complete the surveys.

Data Analysis. Groups 1, 2, and 3 will be described with respect to baseline characteristics (e.g., means, standard deviations, ranges, and proportions). Before beginning formal analyses, we will examine the patterns of missing data, paying special attention to the balance of missing data in the study arms. From our prior trials, we anticipate all participants will provide baseline data, 90% will provide immediate post-intervention data, and approximately 80% will complete the 6 and 12 month post-enrollment assessment. Analysis of Intervention Effects.

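### The primary outcome is a six-month look-back from the survey date, not a count from randomisation, and does not expressly exclude the study's own baseline HIV test (minor)

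*Combined protocol and SAP*

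**What the plan says.** The outcomes statement that closes the Reminder notifications and retention text begins "The primary outcome for Aim 2 / study trial (Uptake of rapid HIV" and continues "self-testing) is the proportion of participants who self-report being tested for HIV in the past 6 months". That sentence gives no start date, names no survey and excludes no test. Just before it the plan notes: "The survey items are included in the Qualtrics attachment". That attachment is not among the documents.

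Follow-Up Surveys places the surveys 6 and 12 months after the baseline visit, in person or by emailed link. It gives no completion window.

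Hypothesis 1 under Aim 2, and the logistic models under Data Analysis, use fixed periods: the first six months, and months 7-12.

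Every randomised participant has a study-administered HIV test first. Eligibility criteria require participants to "receive a non-reactive result on the rapid HIV test at the baseline visit". Study Enrollment says "Prior to enrollment into the RCT participants will be consented to screen and administered a rapid HIV test to determine eligibility", and then "If they are non-reactive they will be randomized and enrolled into the trial". The Alternatives and Potential Limitations text that follows Randomization adds: "HIV testing will be included as the final screening component to verify study status prior to enrolling".

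Reminder notifications tells arm 1 to use the app and "the HIV self-test kit at 3 months, 6 months, 9 months, and 12 months after enrollment", with a reminder two weeks before and one week after each date.

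**The concern.** The look-back runs from the day the survey is completed, while Hypothesis 1 runs from trial entry. The two agree only when the survey is on time. Two things can then go wrong.

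First, the baseline test lies exactly six months before the due date of the 6-month survey. If that survey is completed early, or the participant places the test later than it was, a truthful-seeming yes can refer to a test that the study itself gave before randomisation. All arms receive it, so it favours neither arm. But the control arm is expected to have more people with no other test, so counting it raises the control rate more and narrows the contrast. It bears only on the first period: at the 12-month survey it is well outside the look-back.

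Second, arm 1 has a scheduled test at month 6, on the boundary between the two periods. A late 6-month survey can count a test taken after month 6 towards the first period. An early 12-month survey reaches back past month 6, so one test could be reported in both surveys. Arm 2 has no such schedule, so misplacement need not be equal between arms.

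A bare yes/no answer cannot be re-scored at analysis, because it does not show which test the participant had in mind.

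**Working it through.** **Inputs.** From Statistical power and sample size calculation: 210 per arm in the primary comparison, 20% attrition, testing rates over six months of 40% (control) and about 60% (app), two-sided alpha 0.05, and at least 80% power claimed for Hypothesis 1 with its two tests.

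**The plan's own figure.** Evaluable per arm: 210 x 0.8 = 168. Two-proportion z test with pooled variance under the null:

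- SE0 = sqrt(2 x 0.5 x 0.5 / 168) = 0.05455
- SE1 = sqrt((0.4 x 0.6 + 0.6 x 0.4) / 168) = 0.05345
- z = (0.20 - 1.96 x 0.05455) / 0.05345 = 1.74, so power = 95.9% per test

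If both tests must succeed and are independent, power is 0.959 x 0.959 = 92.0%. The claim of at least 80% is met.

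**Effect of counting the baseline test.** Let f be the share of participants with no later test who report the baseline test, equal in both arms. f is my assumption; no document gives it.

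- Control rate: 0.40 + 0.60f
- App rate: 0.60 + 0.40f
- Difference: 0.20 x (1 - f)

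| f | Control | App | Difference (points) | Power, first period |
|---|---|---|---|---|
| 0 | 40% | 60% | 20 | 95.9% |
| 0.10 | 46% | 64% | 18 | 91.6% |
| 0.20 | 52% | 68% | 16 | 85.3% |
| 0.25 | 55% | 70% | 15 | 81.3% |
| 0.30 | 58% | 72% | 14 | 77.0% |

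Power for this comparison alone reaches 80% at f of about 0.27. The plan's claim covers two tests. If both must succeed and are independent, and the second is unaffected at 95.9%, the first needs 0.80 / 0.959 = 83.4%, which is reached at f of about 0.22.

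**Off-schedule surveys.** I give no figure. The power section names a Poisson distribution, and a constant testing rate would yield tidy numbers. But arm 1 is told to test at months 3, 6, 9 and 12, with reminders, so its tests should cluster around those dates. A constant rate does not describe that, and the documents give neither survey timing nor the spread of test dates.

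**The case against.** The documents largely settle the intended meaning. Hypothesis 1 concerns testing during the trial, the screening test comes before enrolment and randomisation, and the analysis text uses the fixed periods. On-time surveys make the look-back and the periods coincide. This stands: a reader might infer that the outcome conflicts with Hypothesis 1, or that the screening test is meant to count, and the text supports neither.

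The survey item may already exclude the study test or ask for dates. This also stands, and it is why the first step is a check.

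Surveys are sent at six months, so drift should be mainly late, which moves the baseline test out of the look-back. Early completion is not planned, and no recall-error rate is given. This weakens the main route to dilution but does not close it, because no window is stated.

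A reader might also infer from the label, which speaks of self-testing, that only self-tests count. Hypothesis 1, the power section and Data Analysis all refer to HIV testing in general, and Design Overview gives arm 2 information only, with no home kits. A 40% control rate fits any HIV test far better. One clarifying phrase is enough.

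What remains is that no available passage excludes the screening test or anchors the answer to randomisation.

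**Conclusion.** The point holds as a minor gap in the primary outcome definition. The look-back matches Hypothesis 1 on schedule, but nothing ties it to randomisation, and a test given to everyone before randomisation sits on its edge without being expressly excluded.

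The effect is a possible dilution of the first-period contrast to 20 x (1-f) points. Power for that comparison stays above 80% unless more than about 27% of otherwise-untested participants report the baseline test (about 22% if both Hypothesis 1 tests must succeed and are independent). These figures assume that f is equal across arms and that the planned 40% and 60% are right. A reader might infer from the table that the trial will lose power; the documents do not support this, because they give no value for f. Nor do they allow any size, or a claim of no effect, for arm 1 tests misplaced around month 6.

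**What to change.** In the outcome definition, state that the first-period outcome is at least one HIV test of any type after the randomisation visit and through month 6, excluding the study's screening test. State that the second-period outcome is at least one HIV test in months 7-12.

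Then check the Qualtrics item. If it does not already do so, anchor the 6-month question to *since your baseline visit, not counting the test we gave you*, and the 12-month question to *since month 6*. Ask for the month of the tests, so that those near the month-6 boundary can be assigned to the right period by reported timing and not by the survey date.

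The cost is one or two sentences in the plan and, if the check shows a need, slight rewording of the survey. The downside is some error in recalled dates: the recall problem that could admit the baseline test also affects the months reported. Naming the baseline test in the question deals directly with the main risk.

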Step 3. Review with YAB. Drs. [name] and [name] will facilitate the review of the mLab App user interface, content, and function with the YAB. Through our review, we will ensure that the mLab App is culturally appropriate for both YMSM and YTGW. [name] will insert changes directly into the mLab App mock-ups viewed on a screen, supplemented by note-taking by study staff and audio-recorded. This allows us to confirm meaning, make revisions as necessary, and reach consensus with the YAB. [name] will probe for further discussion on feasible ways forward and to ensure that the mLab App meets the current prevention guidelines. We will incorporate the recommended changes. As a final step, we will have members of the YAB test the final mLab App after the meeting in their own settings (e.g., Home) and return any comments or additional edits within 2 weeks. Final recommendations for the user interface will be shared with [name], who will work with his team and the graphic design team at Little Green Software (see letter of support) to make the final updates to the app.

Aim 2: Evaluate the efficacy of the mLab App in improving both HIV testing rates and linkage to care versus standard preventive care in 525 Black, Latino and other young men and transgender women (inclusive of YMSM and YTGW age 18-29 years) in a 12-month multi-site trial, with randomization at each site to three groups arm 1: intervention (mLab App) (N=210); arm 2: standard of care HIV information control arm (N=210); arm 3: OraQuick home test kits only (N=105).

Hypothesis 1. Youth randomized to the mLab App arm, as compared to youth in the standard of care HIV information control arm, will have: a) increased rates of HIV testing within the first 6 months of the trial; and b) increased rates of re-testing in months 7-12 of the trial.

Hypothesis 2. The total number of youth who test HIV positive and link to care in the mLab App arm will be greater as compared to the standard of care HIV information control arm.

Hypothesis 3. The image processing in the mLab App will: 1) have no statistically significant difference in sensitivity or specificity when compared to confirmatory testing, 2) have greater sensitivity and specificity when compared to the user-submitted self-analyses.

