Design Overview. A randomized controlled trial will be conducted with 525 young men over 12 months. Participants will be randomly assigned to the mLab App arm 1 (intervention) or a control arm 2 (standard of care HIV testing information arm) or arm 3 (OraQuick HIV home tests).¹²⁷ Participants in arm 1 will receive access to the mLab app and HIV home test kits, those in arm 2 will receive standard of care HIV information only. The primary comparison will be between arms 1 and 2. Participants in arm 3 will receive HIV home tests kits, but not access to the mLab app. Participants in all arms will receive standard preventive care at baseline. **Recruitment.** Our recruitment activities will mirror those described in Aim 1. Step 2. We will recruit youth from both Chicago and NYC as well as the entire state of Illinois and neighboring states of Wisconsin,

Michigan and Indiana in the Midwest; and all of the state of New York and neighboring states of Connecticut and New Jersey. We will recruit on Grindr and other social media using banner or pop-up ads that target YMSM and YTGW from these areas.

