Sample. Our sample will include 525 Black, Latino, and other young men and transgender women (inclusive of YMSM and YTGW aged 18-29 years), with Chicago: N=180 and New York: N =345; representing the population size of each city.¹²⁸ **Statistical power and sample size calculation.** This study will use a 2:2:1 RCT design. We plan to recruit total 525 subjects (210, 210, and 105 will be in arm 1, 2, and 3, respectively). The power and sample size calculations are based on the comparison of HIV testing rates in the mLab App arm compared to the standard of care HIV information control arm for Hypothesis 1 (i.e., compare HIV testing at 6 months and re-testing during 7 to 12 months). We calculated the statistical power to detect a difference across all participants (YMSM and YTGW). Our study is not powered to detect differences in outcomes in YMSM and YTGW separately but we will analyze differences in effect by gender identity (see Data Analysis Section below). The effect size is calculated based on the findings from the FORTH RCT⁷⁵ in which self-testing resulted in a two times increase in frequency of HIV testing in high-risk MSM, and a nearly four times increase in non-recent testers compared with standard care, without reducing the frequency of facility-based HIV testing. Using a Poisson distribution, we estimated a 40% HIV testing rate over 6 months for the control group and approximately 60% HIV testing rate for the intervention group. We are using a more conservative effect size than the one **reported** previously by assuming 60% testing rate for the intervention as compared to 85% in the FORTH RCT study.⁷⁵ This 20% difference is equivalent to a medium effect size. All power calculations are based on alpha=0.05 and two-sided tests of the primary comparison and an attrition rate of 20% at 6 and 12 months. We will have at least 80% power for Hypothesis 1, to conduct two tests simultaneously (i.e., to compare HIV testing rate during the first 6 months and to compare re-testing rate during 7 to 12 months).

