Recruitment for study participation will occur following approval by the CUMC IRB. The PI will determine eligibility for inclusion, explain the purpose of the study, answer any questions, and obtain written consent from the participants.

Patients who agree to participate will sign a consent form. Recruitment strategies will be developed in collaboration with clinics and community centers. Potential risks and strategies for risk management will be carefully explained as part of informed consent procedures. All HIPAA requirements will be applied to this study. The study plan, advertisements or recruitment letters, lay description of the study, and all consent forms will be submitted to the IRB following proposal acceptance and prior to study initiation. The study PIs will be responsible for obtaining IRB approval for this study.

We will inform the study participants upon enrollment that the goal of the mLab App is for self-testing and NOT for partner testing/sero-sorting. We will advise participants upon study enrollment and consent that the technology is NOT to be used for their partners during the study. Given this limitation, we will suggest that participants who have partners who are interested in testing should contact the study team for more information on HIV testing.

We will also remind participants that the mLab App is not an approved diagnostic test and recommend seeking confirmatory testing (for both negative and positive test results). Upon receiving a positive HIV test result, study participants will then be directed to another screen on their smartphone with the phone number of the Comprehensive Care Program Warm Line. Participants will be told that this result does not necessarily indicate that they are HIV-positive but that further follow-up testing is needed. Participants will also be advised to contact the Clinic or the study team within 24 hours of receiving a positive test result. The number and nature of calls from participants to the study team (e.g., related to mLab App use, test interpretation, distress at reactive results) will all be recorded. All participants will be advised to test quarterly, and will receive the referral number to the Comprehensive Care Clinic.

b. Protections against Risks

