4. There is a risk of receiving a false positive test result, meaning they have tested HIV positive, but are in fact HIV negative. They will be instructed on the limitations of the OraQuick Test, including that false positive results have occurred, which again stresses the need for confirmatory testing since results may change. Limitations of the OraQuick Test: A potential risk of the study is that the participant might mistakenly believe that the test kit protects them against HIV and/or other STIs. It is important that they know that self-tests will not protect them against HIV or other sexually transmitted diseases or infections, and they must use protection such as condoms when engaging in sexual intercourse if they want to avoid infection. HIV testing also does not include testing for STIs. A positive result from the OraQuick Test generally indicates that HIV antibodies have been detected in their body. There is a small risk that a positive result is a mistake. Fewer than 1 in 100 people who get tested may receive an incorrect result. Therefore, if they test positive, a second test is needed to confirm the result. If participants receive a HIV positive result while testing during this study, the study team will provide them with confirmatory testing. A negative result in the OraQuick test generally means that HIV has not been detected in their body and that they are HIV uninfected. A negative result could also mean that the participant may have gotten HIV too recently for the test to detect it. Additional HIV testing will be made available to all subjects.
5. A risk of taking part in this study is the possibility of a loss of confidentiality or privacy, including that associated with the mLab app on their phone. Loss of privacy means having their personal information shared with someone who is not on the study team and was not supposed to see or know about their information. The study team plans to protect the participants' privacy by storing all data on locked computers in locked facilities on secure servers hosted by Columbia University Medical Center. The servers are HIPAA compliance and set to conform to the current industry standards for storing Personal Health Information (PHI)

BENEFITS:**Potential Benefits of the Proposed Research to Human Subjects and Others**

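### The primary outcome is labelled uptake of HIV self-testing but defined as any self-reported HIV test, and the definition does not exclude the study's own screening test

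*Combined protocol and SAP*

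**What the plan says.** The outcome paragraph of Aim 2 (end of the retention text, before Follow-Up Surveys) opens "The primary outcome for Aim 2 / study trial (Uptake of rapid HIV" and continues "self-testing) is the proportion of participants who self-report being tested for HIV in the past 6 months". The first part is the label and the second is the definition. The definition sets no test type, setting or exclusion.

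The rest of Aim 2 speaks of HIV testing in general. Hypothesis 1 predicts "a) increased rates of HIV testing within the first 6 months of the trial" and more re-testing in months 7-12. The sample size section says "we estimated a 40% HIV testing rate over 6 months for the control group", against about 60% in the intervention arm. The Data Analysis section fits logistic models to HIV testing and re-testing. Under Design Overview, "those in arm 2 will receive standard of care HIV information only", so arm 2 has no kits.

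Two other places focus on the self-test itself. The trial title names it, and the summary list under Theoretical Framework makes its uptake the most important question for the technology.

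Study Enrollment and the Aim 2 eligibility criteria give every participant a rapid HIV test at the baseline visit, and only those with a non-reactive result are randomised. The first follow-up survey comes six months after that visit. The survey items are in an attachment that is not part of the documents.

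**The concern.** A primary outcome should be called what it measures. Here the label would let a report claim that the app raised self-test uptake, when the variable behind the claim also counts clinic and provider tests. A participant who never opened a kit but was tested at a clinic is a success.

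Two consequences follow. First, the main result alone cannot answer the question the Background puts first. Nor can it show whether home tests replace facility visits, which the section on the scientific premise for self-testing raises as a concern. Second, nothing stops a participant from truthfully counting the screening test as a test in the past six months. Every participant in every arm had one, so counting it pulls both rates up and the difference down.

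**Working it through.** **1. Which outcome do the operative sections use?**

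| Place | What is counted |
|---|---|
| Outcome label (Aim 2) | self-testing |
| Trial title; summary list under Theoretical Framework | self-testing |
| Outcome definition (Aim 2) | any HIV test |
| Hypothesis 1 | any HIV test |
| Power calculation, 40% and 60% | any HIV test |
| Logistic models (Data Analysis) | any HIV test |

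The 40% control rate settles the matter. Arm 2 receives no kits, so a rate of 40% is plausible only if tests from other sources count. A self-test-only outcome would be near zero in arm 2 by design. With assumed control rates of 1-5% and intervention rates of 20-60%, power would be 98.8% or more, but the contrast would largely reflect that only one of the two arms was given kits.

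**2. The plan's own power figure.** Inputs from the sample size section: 210 per arm, 20% attrition, 40% against 60%, two-sided alpha 0.05.

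- Evaluable per arm: 210 × 0.80 = 168.
- Standard error under the null: √(2 × 0.5 × 0.5 / 168) = 0.0546; times 1.96 = 0.1069.
- Standard error under the alternative: √((0.24 + 0.24) / 168) = 0.0535.
- z = (0.20 − 0.1069) / 0.0535 = 1.74, so power is 95.9% per test.
- Power to win both tests, if independent: 0.959² = 92.0%.

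The stated floor of 80% holds for the any-test outcome.

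**3. The screening test.** The test is done at the baseline visit and the first survey comes six months after that visit, so it lies on the boundary of the recall period. Let x be the share of otherwise untested participants, equal in both arms, who report it.

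- Intervention: 0.60 + 0.40x. Control: 0.40 + 0.60x.
- Difference: 0.20 × (1 − x).

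| x (assumed) | Intervention | Control | Difference |
|---|---|---|---|
| 0 | 60% | 40% | 20 points |
| 10% | 64% | 46% | 18 points |
| 25% | 70% | 55% | 15 points |
| 50% | 80% | 70% | 10 points |
| 100% | 100% | 100% | 0 |

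Only the first window is exposed. At the 12-month survey the screening test is a year old.

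**4. Analyses that need test type.** The plan will check arm 1 self-report against test photographs. Under an any-test definition, a reported test without a photograph may be a genuine clinic test, so misreporting cannot be told from testing elsewhere. The comparison of arms 1 and 3 is meant to show what the app adds to kit distribution, and kit use is the most direct measure of that.

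**The case against.** The strongest reply is that this is a mislabel and nothing more. The definition, hypothesis, planning rates and models all agree on any HIV test. That stands: there is one operative outcome, and a self-test-only outcome would be a poorer test of Hypothesis 1. It is also fair that the survey attachment may already ask where and how each test was done, or anchor recall to the baseline visit. Even so, the outcome definition and the analysis plan make no use of such items.

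A reader might go further and infer that study-offered testing contaminates the control rate and leaves the trial underpowered. Participants are "to be offered HIV testing referral information and on-site testing through existing service providers", one sentence says "Additional HIV testing will be made available to all subjects", and "All participants will be advised to test quarterly". The documents do not support that inference.

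- The on-site testing is through existing providers, in a sentence about continuing normal healthcare. It reads as usual care for participants in general, so it belongs in the comparator and randomisation protects the comparison.
- The sentence on additional testing stands in a list introduced for the intervention arm. Parallel text in the risk sections ties such testing to a request by someone who tested negative.
- In an arm without kits, the 40% must come largely from provider testing already. Adding take-up on top may count it twice, and the documents give no take-up rate. At an assumed 25% (70% against 55%), power per test is still 81.3%. It falls below 80%, to 66.2%, only if the requirement is to win both tests and the two are independent.

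Nor does it follow that every test arranged by the study should be excluded. If on-site tests were classed that way, usual-care testing would be removed from arm 2 while kits still counted in arm 1, which would favour the app.

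**Conclusion.** The point holds as a defect of naming, definition and reporting. The randomised comparison of any HIV test is valid and its stated power is met (95.9% per test). What the plan cannot support as written is a conclusion about self-test uptake, or about substitution for facility testing, because no outcome separates the two.

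The open screening test is the one part that could change the estimate. It would shrink the first-window difference in proportion to the share who report it, from 20 points to 20 × (1 − x). That rests on equal reporting in both arms and on survey wording that cannot be seen here. If the items already exclude the baseline test, this part reduces to stating the exclusion in the definition.

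**What to change.** - Rename the primary outcome: any HIV test since the baseline visit, in months 0-6 and in months 7-12.
- State that the screening test and any test done at a study visit do not count, and that ordinary clinic and provider testing counts in all arms.
- If the survey attachment does not already do so, record the place and type of each test at 6 and 12 months.
- Report home-kit use and facility-based testing as separate secondary outcomes by arm. The first shows self-test uptake and supports the photograph check and the comparison of arms 1 and 3; the second shows any substitution. The Arm 1 text advises confirmatory testing after either result, so identify facility tests that follow a home test.

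The cost is a change of definition and one or two more items in surveys already planned. Sample size and primary models stay as they are.
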